National Institutes of Health (NIH)-funded investigators and clinical trial site staff who are responsible for the conduct, management, or oversight of NIH-funded clinical trials have completed Human Subjects Protection and ICH GCP Training.

The protocol, informed consent form(s), recruitment materials, and all participant materials will be submitted to the Institutional Review Board (IRB) for review and approval. Approval of both the protocol and the consent form must be obtained before any participant is enrolled. Any amendment to the protocol will require review and approval by the IRB before the changes are implemented to the study. In addition, all changes to the consent form will be IRB-approved; a determination will be made regarding whether a new consent needs to be obtained from participants who provided consent, using a previously approved consent form.

Glossary of Abbreviations

AE	Adverse event
ALT (SGPT)	Alanine transaminase (serum glutamate pyruvic transaminase)
AML	Acute myeloid leukemia
ANC	Absolute neutrophil count
AST (SGOT)	Aspartate transaminase (serum glutamic oxaloacetic transaminase)
B-HCG	Beta human chorionic gonadotropin
BMT	Bone marrow transplant
CBC	Complete blood count
CFR	Code of Federal Regulations
CNS	Central nervous system
CR	Complete response
CRc	Cytogenetic complete remission
CRi	Complete remission incomplete
CRm	Morphologic complete remission
CRF	Case report form
CST	Central standard time
СТ	Computed tomography
CTCAE	Common Terminology Criteria for Adverse Events
CTEP	Cancer Therapy Evaluation Program
DLT	Dose limiting toxicity
DNA	deoxyribonucleic acid
DSM	Data and Safety Monitoring
DSMC	Data Safety Monitoring Committee
ECG (or EKG)	Electrocardiogram
ECOG	Eastern Cooperative Oncology Group
EDTA	ethylenediaminetetraacetic acid
FDA	Food and Drug Administration
FISH	fluorescent in situ hybridization
FWA	Federal wide assurance
GCP	Good Clinical Practice
HHS	Department of Health and Human Services
HIV	Human Immunodeficiency Virus
HRPO	Human Research Protection Office (IRB)
IND	Investigational New Drug
IRB	Institutional Review Board
MDS	Myelodysplastic syndrome
MM	Multiple myeloma
MRI	Magnetic resonance imaging
MTD	Maximum tolerated dose
NCCN	National Cancer Center Network

NCI	National Cancer Institute
NIH	National Institutes of Health
NSCLC	Non-small cell lung cancer
OHRP	Office of Human Research Protections
ORR	Overall response rate
OS	Overall survival
PBMC	Peripheral blood mononuclear cell
PD	Progressive disease

APPENDIX D: Washington University Unanticipated Problem Reporting Cover Sheet	40
APPENDIX E: Study-Specific DSM Tables	41

PROTOCOL SUMMARY

Title:	Pre-operative Adaptive Short Course Radiation Therapy in Gastric Cancer					
Study Description:	Hypothesis : Adaptive radiation therapy followed by sequential multi- agent chemotherapy will result in a pathologic complete response (pCR) of at least 20%.					
	In this study, patients with gastric adenocarcinoma will receive hypofractionated adaptive radiation therapy followed by total neoadjuvant chemotherapy followed by surgery.					
Objectives:	Primary Objective: To quantify the pCR rate in gastric cancer patients treated with preoperative radiation followed by total neoadjuvant chemotherapy.					
	 Secondary Objectives: To quantify the proportion of patients able to complete a full course of total neoadjuvant chemotherapy To quantify the local control rate of gastric cancer patients treated with preoperative radiation followed by chemotherapy. To quantify the toxicity of gastric cancer patients treated with preoperative radiation followed by chemotherapy. To quantify the overall survival in gastric cancer patients treated with preoperative radiation followed by chemotherapy. To quantify the disease-free survival in gastric cancer patients treated with preoperative radiation followed by chemotherapy. 					
	 Exploratory Objectives: To quantify the deviation in dose to the tumor due to variation in stomach position. To quantify the deviation in dose to the nearby OARs due to variation in OAR position. To determine the distribution of TCGA molecular subtypes in gastric adenocarcinoma after radiation and chemotherapy. To identify differentially expressed post-treatment biomarkers in gastric tumors. To correlate circulating tumor DNA (ctDNA) levels with clinical outcomes. 					
Endpoints:	Primary Endpoint: The rate of pCR (both ypT and ypN) in gastric cancer patients treated with preoperative radiation followed by total neoadjuvant chemotherapy.					
	Secondary Endpoints: 1. Proportion of patients able to complete a full course of total neoadjuvant chemotherapy					

	2. The local control rate at 1 year post RT.			
	3. The rate of grade 3 or greater toxicity as defined by CTCAE v			
	5.0			
	4. The overall survival at 1 year post RT.			
	5. The disease-free survival at 1 year post RT.			
	Exploratory Endpoints:			
	1. Average percent difference in coverage of PTV by 95% isodose			
	line.			
	2. Average percentage difference in dose to nearby OARs (i.e.			
	duodenum, small bowel, large bowel) due to variation in OAR			
	position.			
	3. The percentage of patients in each TCGA molecular subtype			
	after radiation and chemotherapy.			
	4. The specific biomarkers			
	5. ctDNA levels			
Study Population:	Thirty-six adults of any gender who have a diagnosis of gastric cancer			
	and are receiving preoperative radiation followed by total neoadjuvant			
	chemotherapy will be enrolled.			
Phase:	Not applicable.			
Description of Sites /	This is a multicenter trial coordinated by and enrolling at Washington			
Facilities Enrolling:	University in St. Louis. The study will also open to enrollment at other			
	sites in the U.S.			
Description of Study	Patients undergoing preoperative radiation and chemotherapy for			
Intervention:	gastric cancer will undergo simulation for radiation treatment planning			
	on a conventional referenced CT scanner and ViewRay or Ethos			
	treatment machines. High resolution volumetric MR or CBCT images			
	will be acquired daily in the treatment position and OARs contoured by			
	the radiation oncologist. The new electronic density map will be used			
	to recalculate dose from the initial radiation plan (based on CT/MR			
	simulation) and treatment delivered to maximize coverage while not			
	exceeding dosimetric constraints.			
Study Duration:	36 months.			
Participant	12 months.			
Duration:				

SCHEMA

Eligible Patients Diagnosis of gastric adenocarcinoma

Treatment Plan

Adaptive 25 Gy / 5 fractions

followed by

Total neoadjuvant chemotherapy

followed by

Surgery

1.0 SCHEDULE OF ACTIVITIES

Bereening pro		t tane place	, ,, ,,,,,,,,,,,,,,,,,,,,,,,,,,,,,,,,,,	100 44	. ,,,,,	egibtita						
	Screening	Baseline	Fx1	Fx2	Fx3	Fx4	Fx5	Chemo ⁴	Surgery ⁵	3-mo F/U ⁶	6-mo F/U ⁶	12-mo F/U ⁶
Informed consent	Х											
H&P, ECOG PS	Х									Х		
CBC w/diff ¹	Х											
CMP ¹	Х											
Pregnancy test ²	Х											
EUS	Х											
Institutional MRI	Х											
screening questionnaire	Λ											
Simulation		Х										
CT C/A/P		Х							X^8		Х	Х
PET/CT		\mathbf{X}^{11}										
Adaptive SCRT ³			Х	Х	Х	Х	Х					
SOC chemotherapy ¹⁰								Х		Х		
Gastrectomy									X ⁹			
Research blood for		Х						X^7	X ⁷		X ⁷	
ctDNA		Λ						Λ	Λ		Λ	
AE assessment	AEs will be tracked from baseline through 12 months after surgery/definitive											
	end of treatment. Refer to Section 8.0 for more details.											

Screening procedures must take place within 60 days of registration.

1. labs will be drawn as per SOC

2. women of childbearing potential only

3. patients will receive 5 fractions of radiotherapy delivered once daily; radiotherapy may take up to 10 business days (due to logistical delays)

4. SOC chemotherapy will begin 2-4 weeks after completion of radiotherapy

5. within 2-4 weeks after completion of SOC chemo

6. follow-up visits will take place at 3 months (+/-2 weeks), 6 months (+/-4 weeks), and 12 months (+/-4 weeks) post-surgery; patients who don't undergo surgery will have follow-up visits at 3 months (+/-2 weeks), 6 months (+/-4 weeks), and 12 months (+/-4 weeks) from the date of definitive end of treatment.

7. after completion of RT / prior to starting chemo, at completion of chemo / prior to surgery, and 6 months after surgery. See Section 9.2 for further details.

8. prior to surgery

9. tissue for research will be collected from patients who experience pCR

10. Any SOC total neoadjuvant chemotherapy regimen may be given at the discretion of and under the supervision of the treating medical oncologist

11. PET/CT is strongly encouraged at baseline but optional

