9.0 CORRELATIVE STUDIES

9.1 Tissue for Research

Patients with pCR will have normal gastric tissue collected at the time of surgery. Fresh tissue will be formalin-fixed and paraffin-embedded (FFPE) per institutional standards.

RNA and whole exome sequencing will be used for formalin-fixed, paraffin-embedded, post-treatment gastric adenocarcinoma tissue samples to determine the post-treatment patient distribution amongst the TCGA molecular subgroups. Blocks will be reviewed by institutional pathologists, H&E slide prepared to identify the block with highest tumor volume and grade (ideally tumor samples with $\geq 60\%$ tumor nuclei and $\leq 20\%$ necrosis will be processed for nucleic acid extraction³⁸) and then the corresponding block sent for biomarker analysis. Normal tissue adjacent to tumor will also be obtained for differential expression analysis. FFPE tissue will be packaged in insulated Styrofoam packaging and shipped to and sequencing performed at the Washington University Genome Technology Access Center. Cold packs and dry ice are not necessary for FFPE tissue samples. Shipping address is:

Genome Technology Access Center [name]

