11.0 MEASUREMENT OF EFFECT

Effect will be measured by the rate of pCR (primary and nodal) found at the time of surgical resection. Partial pathologic response will be defined as < 10% viable tumor remaining. Residual disease will be documented in the form of % treatment response and % viable tumor. No radiographic response to treatment will be recorded or assessed.

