14.0 STATISTICAL CONSIDERATIONS

14.1 Statistical Hypotheses and Sample Size Determination

Chemotherapy alone has a pCR rate of 6-16%¹⁰. PCR is defined as a pathologic complete response (no tumor on gastrectomy specimen). We hypothesized that preoperative radiation followed by chemotherapy would result in a pCR rate of 20%, and with 36 patients, our confidence interval for this estimate will fall between 9% and 37%.

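### Schedule note 9 assigns research tissue to patients with pCR, who have no tumor, and conflicts with the tumor sequencing planned in Section 9.1

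*Combined protocol and SAP*

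**What the plan says.** Section 1.0, note 9, attached to the gastrectomy row: "tissue for research will be collected from patients who experience pCR". No other entry in the schedule mentions tissue.

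Section 9.1, first paragraph: "Patients with pCR will have normal gastric tissue collected at the time of surgery". That tissue is described as fresh and then formalin-fixed and paraffin-embedded (FFPE).

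Section 9.1, second paragraph, turns to tumor. Sequencing is planned on "post-treatment gastric adenocarcinoma tissue samples to determine the post-treatment patient distribution amongst the TCGA molecular subgroups". For block selection: "Blocks will be reviewed by institutional pathologists, H&E slide prepared to identify the block with highest tumor volume and grade", and "then the corresponding block sent for biomarker analysis". Normal tissue next to the tumor is also to be obtained. The paragraph does not say which patients these steps apply to or when their tissue is collected.

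Section 14.1: "PCR is defined as a pathologic complete response (no tumor on gastrectomy specimen". Section 11.0: "Effect will be measured by the rate of pCR (primary and nodal) found at the time of surgical resection".

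Exploratory objectives 3 and 4 (Protocol Summary and Section 3.0) are the distribution of TCGA subtypes after treatment and the differentially expressed biomarkers in treated gastric tumors. Section 10.0 makes the Research Tissue Form due at surgery. The specimen table in Appendix E has a tissue row at surgery and a column for the number of eligible patients, without saying who is eligible.

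**The concern.** Both exploratory tissue objectives need residual adenocarcinoma. The schedule is what site staff work from, and its one tissue line names the group that by definition has none. A coordinator who follows it would flag the pCR patients and have no prompt to retrieve tumor blocks from the rest. A coordinator who works from the second paragraph of 9.1 would retrieve blocks from patients whom note 9 does not mention. The trial is multicenter, so the set of sequenced tumors could come to depend on which text each site followed. The collection percentage reported to the monitoring board would have no fixed denominator.

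The second problem is timing. Section 9.1 makes a sample taken at surgery conditional on pCR, and pCR is a pathology result.

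**Working it through.** **Inputs.** n = 36 (Section 2.3.1). Hypothesized pCR rate 20%, stated interval 9% to 37% (Section 14.1), 95% level (Section 14.2). The documents give no resection rate, so 70% to 90% is an assumption, shown as a range beside full resection.

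**The plan's own figure.** With x = 0.20 × 36 = 7.2, the exact Clopper-Pearson 95% limits are 8.6% and 36.7%, which round to the stated 9% and 37%. The interval reproduces and is not in dispute. It is used below only as a plausible range for the pCR rate.

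**Who falls on each side of note 9.** With N resected patients and pCR rate p, patients with pCR = N × p and patients without pCR = N × (1 − p).

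| Resected N | p | With pCR (named in note 9) | Without pCR (not named in the schedule) |
|---|---|---|---|
| 36 | 9% | 3.2 | 32.8 |
| 36 | 20% | 7.2 | 28.8 |
| 36 | 37% | 13.3 | 22.7 |
| 32.4 (90%) | 20% | 6.5 | 25.9 |
| 25.2 (70%) | 20% | 5.0 | 20.2 |

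Across the whole 9% to 37% range, 70% to 90% resection gives about 16 patients without pCR (25.2 × 0.63 = 15.9) up to about 29 (32.4 × 0.91 = 29.5). These counts are upper limits on usable tumor samples, because 9.1 ideally wants at least 60% tumor nuclei and no more than 20% necrosis.

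**Passages side by side.**

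| Question | Note 9 | 9.1, first paragraph | 9.1, second paragraph |
|---|---|---|---|
| Which patients? | With pCR | With pCR | Not named; only those with residual tumor are possible |
| Which tissue? | Not specified | Normal gastric | Tumor block and adjacent normal |
| When? | Gastrectomy row | At surgery, fresh | After pathologist review of FFPE blocks |

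No passage states the tumor-bearing group as a collection group.

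**Timing.** The primary endpoint requires both ypT and ypN. Section 6.4 mandates a D2 dissection, and the only intraoperative pathology it describes is frozen section for margins. The protocol describes no route by which pCR would be known in the operating room. That it is unknown then is an inference, though a strong one. It bears on the fresh normal sample in 9.1. It does not bear on tumor blocks, which pathologists choose later from fixed tissue.

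**The case against.** The best defense is that the passages can be read as complementary. Note 9 does not contain the word only. Section 9.1 is the section that governs tissue, and it does provide for choosing and sending tumor blocks with adjacent normal tissue. On this reading patients with tumor give an existing block, patients with pCR give normal gastric tissue because there is no block to send, and note 9 merely flags the latter. This stands as far as tumor supply is concerned. A reader might infer from note 9 that the protocol leaves the subtype and biomarker objectives with no tumor samples at all. The documents do not support that, because 9.1 plans for tumor and the patients without pCR are its source.

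The defense does not remove the conflict. Note 9 speaks of research tissue in general and does not limit itself to an extra normal sample. Even on the complementary reading, a site has to deduce from the block-handling steps who gives tumor.

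On timing, it can be said that Section 11.0 itself places the pCR finding at resection, and that the due date in Section 10.0 is a form milestone, with 10 business days allowed to secondary sites for data entry. Both are fair, and the form's due date proves little. They do not help with fresh tissue that must be taken, or not, during the operation.

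It is also fair that Appendix E leaves its tissue denominator unspecified rather than contradictory.

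**Conclusion.** The point holds as a conflict between passages. The schedule's only tissue instruction names patients without tumor, while the exploratory objectives and the second paragraph of 9.1 require patients with tumor and never name them. At 20% pCR with all 36 resected, following the schedule alone reaches about 7 patients and passes over about 29 (about 23 to 33 across the stated 9% to 37%). At an assumed 70% to 90% resection, about 20 to 26 are passed over at 20% pCR. These figures describe a site that relies on the schedule; they do not describe the protocol read as a whole.

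The timing defect is narrower. It concerns the fresh normal sample made conditional on pCR and rests on the inference that ypT and ypN are not known during surgery.

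Only exploratory endpoints are touched. The primary pCR analysis, its interval and the secondary endpoints do not change. The correction is still worth making before sites collect, since the available tumor set is small and blocks not requested may be hard to recover consistently.

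**What to change.** Reword note 9 and the first sentence of Section 9.1 along these lines:

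- Research tissue comes from every patient who undergoes resection.
- After pathology review, the FFPE block with residual adenocarcinoma and adjacent normal tissue is sent for each patient without pCR.
- After pathology review, normal gastric tissue from the resection specimen is sent for each patient with pCR.
- If fresh normal tissue is wanted, its collection does not depend on pCR status.

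In Appendix E, set the tissue denominator to all resected patients.

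The cost is a change to one footnote, one sentence and one table entry, through a protocol amendment that needs IRB approval. The resection specimens are obtained anyway and the sequencing is already described in Sections 9.1.1 and 9.1.2. Taking fresh normal tissue from everyone would add a collection for patients without pCR, so it should be adopted only if the fresh sample is needed.

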2.0 INTRODUCTION

2.1 Study Rationale

Gastric cancer is a global health issue as the world's fifth most common malignancy and third leading cause of cancer mortality, respectively¹. Preoperative radiation therapy may improve overall survival (OS) but is seldom used². There is precedent for preoperative chemoradiation, as it is the standard of care for esophageal and gastroesophageal junction tumors³. However, reluctance of physicians to prescribe preoperative radiation therapy in gastric cancer may be due to the large treatment fields necessary to account for stomach motion. Adaptive radiation therapy may permit decreased field sizes and more accurate dose delivery. In traditional CT based radiation delivery the same radiation plan is delivered each day without assessment of inter-fraction or intra-fraction motion. Adaptive radiation therapy permits the physician to contour the unique anatomy daily to generate a new plan to account for day to day organ motion. Real-time imaging is also used during the treatment so that radiation therapy may overcome traditional barriers of radiation delivery in gastric cancer and improve oncologic outcomes.

Short course radiation therapy (SCRT) is an increasingly used treatment modality. In rectal adenocarcinoma, SCRT followed by chemotherapy results in double the pathologic complete response (pCR) as long course chemoradiation⁴. SCRT also allows the patient to proceed to multiagent chemotherapy sooner, as the concurrent chemotherapy delivered with long course chemoradiation is usually single agent or decreased systemic dosing. Thus preoperative SCRT followed by chemotherapy may permit more downstaging, pCR and decrease metastatic spread in gastric adenocarcinoma.

2.2 Background

2.2.1 Gastric Cancer

Gastric cancer is a global health issue with 952,000 new cases and 723,000 deaths in 2012, ranking as the world's fifth most common malignancy and third leading cause of cancer mortality, respectively¹. Perioperative chemotherapy followed by gastrectomy is the category 1 treatment recommendation in the National Comprehensive Cancer Network (NCCN) guidelines⁵ for locoregional disease, based on the results of the MAGIC and FLOT trials⁶. The role of radiation therapy in gastric cancer is supported in the adjuvant setting and improves OS, relapse free survival and local failure^{7,8}. However, postoperative radiation fields are large and cause significant side effects, with reports of up to 32% acute grade 4 toxicity⁶.

Gastric cancer patients with a pCR to preoperative chemoradiation therapy have an improved OS^{2,9}. Despite large randomized studies indicating that pCR is rarely achievable with neoadjuvant chemotherapy alone¹⁰, preoperative chemoradiation remains a category 2B recommendation in NCCN guidelines. There is precedent for preoperative chemoradiation, as it is the standard of care for esophageal and

gastroesophageal junction tumors³. Single arm studies have shown pCR rates of 16-30%^{2,11,12}. Reluctance of physicians to prescribe preoperative radiation therapy in gastric cancer may be due to the large treatment fields necessary to account for stomach motion. Nearby OARs, including the heart, lungs, kidneys, liver, small and large bowel, limit the treatment dose and field size. Fluoroscopic and CT based studies in gastric lymphoma patients have demonstrated inter- and intra-fraction stomach movement requiring 3 cm margins^{13,14}. Although preoperative chemoradiation therapy in gastric cancer is currently being evaluated in the international cooperative group TOPGEAR trial, traditional large fields are used without adaptation of radiation plans according to stomach movement¹⁵.

2.2.2 Total Neoadjuvant Therapy

Total neoadjuvant therapy is a treatment paradigm frequently used in rectal adenocarcinoma treatment. By delivering all the planned chemotherapy prior to surgical resection, compliance with chemotherapy increases from 50% to 80%¹⁶. Data indicate that this treatment paradigm increases pathologic complete response¹⁷ and even permits patients to undergo nonoperative management (omitting expirative surgery) if there is a clinical complete response^{18–22}. Data for total neoadjuvant therapy in gastric adenocarcinoma are limited. Delivering total neoadjuvant therapy in gastric cancer may increase the amount of chemotherapy tolerated by the patient, allow increased downstaging, and increase the pathologic complete response rate. Further, if this treatment paradigm results in a high clinical and pathologic complete response, it may be an alternative treatment option for those patients not eligible for surgery.

2.2.3 Adaptive Radiation Therapy

The ViewRay system is a MRgRT coupled LINAC machine (ViewRay Inc., Oakwood Village, OH). The 0.35 Tesla real-time MR imaging allows radiation to be delivered to the tumor only when the target is in the designated treatment area. Traditional 3D CT planned radiation contours include a margin to account for respiratory motion, internal organ motion and setup error. MRgRT may permit smaller margins resulting in lower dose to normal structures²³. Daily plan adaptation is possible with physicians contouring OARs, and subsequent changes in beam arrangements or dose to meet dosimetric constraints. Not only can this imaging guided treatment ensure prescribed dose delivery, it may permit dose escalation or boost volumes for gross tumor²³. To date there is no clinical trial that has prospectively evaluated the feasibility or oncologic outcomes of preoperative MRgRT plus concurrent chemotherapy in gastric cancer.

At Washington University, we treat pancreas, liver, breast and other intraabdominal and thoracic tumors with MRgRT. Our preliminary data for stomach motion during definitive (non-operative) radiation treatment of gastric lymphoma (Figure 1) indicate that even with patient instructions for NPO 3 hours prior to treatment, the daily stomach position can vary up to 2.95 cm from the planning position. Motion assessment of 5 patients with gastric lymphoma show a mean translational distance (calculated from x, y and z displacement) of 1.3 ± 0.5 cm. The patients' average stomach volume was 763 cc, with 29.5 ± 19.0 cc outside the 5 mm PTV margin due to daily changes in stomach position over 20 fractions.

To date we have treated four patients with gastric adenocarcinoma with MRgRT 25 Gy in 5 fractions. The patients were treated with this fractionation to palliate symptoms or due to medical inoperability. Patients tolerated the treatment without treatment related acute grade 3+ toxicity. One patient that subsequently underwent sequential chemotherapy and surgical resection was not noted to have increased fibrosis or issues with resectability.

The Ethos system is a cone beam CT (CBCT) based radiation treatment device. It obtains high quality CBCT on-table images that allow the physician to contour the patients anatomy, just as in MRgRT. The Ethos system can be equipped with Identify, that permits surface monitoring of the patient's breathing, allowing CBCT imaging and treatment to be delivered in the same anatomical position. Our data indicate high contour reliability and dosimetric feasibility of adaptive radiation therapy using the Ethos platform^{24,25}. This is a highly reliable adaptive platform alternative to MRgRT.

